9.4 Analysis of Vital Signs and Weights

Vital sign measurements of pulse rate, sitting systolic blood pressure, and sitting diastolic blood pressure will be summarized.

Each vital sign variable and weight will be summarized for all time points (starting with Baseline) with the number of non-missing observations, mean and standard deviation, median, minimum and maximum. Mean change from baseline to each applicable post-baseline visit will be summarized for each vital sign variable, with the number of observations, baseline mean, and visit mean. The change from baseline mean, standard error, and 95% confidence interval will be presented for the mean change from baseline within each treatment group and difference between each elagolix group and placebo.

The number and percentage of subjects who have potentially clinically significant (PCS) vital sign and weight values meeting the following criteria will be summarized by treatment group. All increase/decrease is calculated from Baseline to a post-baseline visit in the Treatment Period.

- Diastolic blood pressure
 - ≤ 50 mmHg and ≥ 15 mmHg decrease
 - > 90 mmHg and ≥ 15 mmHg increase
 - ≥ 100 mmHg
- Systolic blood pressure
 - ≤ 90 mmHg and ≥ 20 mmHg decrease

- ≥ 140 mmHg and ≥ 20 mmHg increase
- ≥ 160 mmHg
- Pulse rate
 - ≤ 45 bpm and ≥ 15 bpm decrease
 - > 100 bpm and ≥ 15 bpm increase
 - ≥ 120 bpm
- Weight
 - $\geq 5\%$ decrease
 - $\geq 7\%$ increase.

Listings will be provided to summarize subject-level vital sign and weight data for subjects meeting PCS criteria.

The number and percentage of subjects who had a sustained PCS vital sign and weight values will be summarized by treatment group and a listing of these subjects will be provided. A sustained PCS value is defined as 3 consecutive PCS values.

9.5 Other Safety Analyses

9.5.1 Columbia Suicide Severity Rating Scale (C-SSRS)

The C-SSRS data will be summarized as observed by treatment group.

The C-SSRS – Baseline/Screening measured at Day 1 will be considered as Baseline C-SSRS. Baseline C-SSRS will be summarized. Other analysis of C-SSRS will only include subjects who have at least 1 post-baseline C-SSRS measurement, regardless of whether they had a baseline C-SSRS measurement. The number of subjects with suicidal ideation, suicidal behavior, and self-injurious behavior without suicidal intent at each scheduled assessment during the appropriate Treatment Period will be summarized. In addition, this table will be repeated for providing a summary of lifetime outcomes and past year outcomes at screening and Day 1. No statistical test will be performed.

The number of subjects with suicide-related treatment-emergent events based on the C-SSRS during the appropriate Treatment Period will be summarized. No statistical tests will be performed.

A listing of subjects with suicidal ideation, suicidal behavior, or self-injurious behavior without suicidal intent based on the C-SSRS during treatment period will be provided.

9.5.2 Bone Mineral Density

All analyses and summaries of bone mineral density (BMD) will be performed for each anatomic location, i.e., femoral neck, lumbar spine, and total hip. For subjects who had a right-side scan performed (rare instances), their data for right femoral neck and right femoral total hip will be included in the analysis with the data for the left femoral neck and left total hip, respectively (available for the majority of subjects). If more than one scan is reported for an anatomic location within an analysis window, the worse (the lower value) of the multiple measurements will be used for analysis for each anatomic location. Unless otherwise specified, the analysis of BMD will exclude subjects who switch machine manufacturer type (Lunar or Hologic).

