DXA scans are required to be performed for all subjects during the Treatment Period at Months 6, 12, 18, 24, 30, 36, 42, and 48 and will be submitted to the central reader for review and analysis. The central reader will be blinded to the subjects' treatment assignment, but not to the corresponding time point.

The window for performing DXA scans at Treatment Months 6, 12, 18, 24, 30, 36, 42, and 48 is \pm 15 days around the respective study visit.

If the results of any post-baseline DXA prior to Month 48, as read by the central reader selected for the study, document either of the following results, the subject must be discontinued from study drug dosing and will enter the Follow-Up Period:

- a Z-score (for subjects < 40 years of age at the time of the Screening DXA) or T-score (for subjects ≥ 40 years of age at the time of the Screening DXA) of < -2.5 in the lumbar spine, total hip or femoral neck OR
- a BMD decrease from baseline of > 8% in the lumbar spine, total hip or femoral neck

If the BMD percent change from baseline of any post-baseline DXA prior to Month 48 cannot be provided by the central reader (i.e., due to scanner changes), then the TA MD must be consulted to confirm if the subject can continue study drug dosing. A BMD decrease at any anatomic region (lumbar spine, total hip **or** femoral neck) that results in discontinuation from the study should be reported as an adverse event (Section 6.1.1).

DXA Scans Performed for Subjects who Prematurely Discontinue in the Treatment Period

DXA scans are required to be performed as part of the Premature Discontinuation visit as follows:

- Subjects who discontinue prior to the Treatment Month 6 visit only if the reason for premature discontinuation is due to the occurrence of a fracture or any newly diagnosed bone condition
- Subjects who discontinue any time at the time of or after the Treatment Month 6 visit, or if one was not performed within approximately 6 months of the PD visit.

However, if a subject is being discontinued from the study due to a Z-score or T-score of < -2.5 in any region, BMD decrease from baseline of > 8% in any region, or TA MD

assessment, additional DXA scans do not need to be performed as a part of the Premature Discontinuation visit procedures. In these circumstances, the subject would enter the Follow-Up Period and continue with required BMD evaluations.

DXA Scans Performed in the Follow-Up Period

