8.1.7.4 Bone Mineral Density

The key BMD assessment comparisons are at the lumbar spine at Month 6 and Month 12. Secondary BMD endpoints include total hip and femoral neck. The elagolix 200 mg BID plus E2/NETA (1 mg/0.5 mg) QD dose will be compared to placebo at Months 6 and 12 and will be compared to Elagolix 200 BID alone at Month 6 based on percent change from baseline.

Percent change from baseline in BMD during Months 13 through 48, as well as Z-score and T-score values will also be summarized.

Full analysis details will be provided in the SAP.

Post-treatment bone mineral density scans will be summarized similarly, as appropriate. Percentage change from baseline in the post-treatment period will be compared with the percentage change from baseline at the end of the treatment period. There will be no statistical testing in the Follow-Up period.

Additional analysis details will be specified in the SAP.

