2.5 End of 12-Month Placebo-Controlled Treatment Period Analysis

An end-of-placebo-controlled treatment period analysis of the primary, secondary and other efficacy variables along with demographic and safety variables will be performed after the last subject completes the 12-Month placebo-controlled Treatment Period. These analyses will include data collected during the Treatment Period (placebo-controlled and open-label Treatment Periods) and the Follow-Up Period up to the data cut-off for the interim lock. The database will be versioned for an interim soft lock and any discrepant data will be clarified before the versioning. Analyses will be performed by AbbVie.

Since this end-of-placebo-controlled treatment period analysis is the only and final analysis of the primary and key secondary endpoints, no additional adjustment of alpha-level is necessary.

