9.5.2.1 Bone Mineral Density during the Treatment Period

BMD

A summary of continuous BMD at each scheduled assessment will be provided during the appropriate Treatment Period. This summary will include the sample size, mean, SD, median, minimum, and maximum. This analysis will be repeated including subjects who switch machine manufacturer type (Lunar or Hologic), for subjects with scans only on Lunar machines, and for subjects with scans only on Hologic machines.

The analysis of percent change in BMD from baseline to each relevant visit during the Treatment Period will be based on an ANCOVA model with treatment as the main effect and baseline value of corresponding parameter as a covariate. Elagolix plus E2/NETA group will be compared to placebo at Months 6 and 12 and will be compared to the

elagolix alone group at Month 6 during the placebo-controlled Treatment Period. In addition, elagolix alone group will be compared to placebo at Months 6 and 12 during the placebo-controlled Treatment Period. This analysis will be repeated including subjects who switch machine manufacturer type (Lunar or Hologic), for subjects with scans only on Lunar machines, and for subjects with scans only on Hologic machines.

The number and percentage of subjects with percent change from Baseline to each scheduled assessment during the Treatment Period in mutually exclusive categories of BMD decrease: $\leq 0\%$, $> 0\% - \leq 1.5\%$, $> 1.5\% - \leq 3\%$, $> 3\% - \leq 4\%$, $> 4\% - \leq 5\%$, $> 5\% - < 8\%$, and $\geq 8\%$ will be summarized by treatment group. Elagolix plus E2/NETA group will be compared to placebo at Months 6 and 12 and will be compared to elagolix alone group at Month 6 during the placebo-controlled Treatment Period using chi-square tests. In addition, elagolix alone group will be compared to placebo at Months 6 and 12 during the placebo-controlled Treatment Period.

The analysis of percent change in BMD from Month 6 to Month 12 during the Treatment Period will be based on an ANCOVA model with treatment as the main effect and Month 6 BMD values of corresponding parameter as a covariate for subjects who have both Month 6 and Month 12 BMD values. Same analyses will be provided for percent change in BMD from Month 6 to Month 18 and Month 24. Each elagolix group will be compared to placebo.

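### The BMD analyses exclude whole subjects for switching DXA manufacturer, with no timing rule, so valid same-manufacturer changes at Months 6 and 12 can be lost

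*SAP*

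**What the plan says.** Protocol 8.1.7.4 states: "The key BMD assessment comparisons are at the lumbar spine at Month 6 and Month 12". The effect on BMD is also one of the three study objectives (Protocol 4.0, SAP 2.1).

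SAP 9.5.2 sets the default for every BMD analysis that has no other rule: "the analysis of BMD will exclude subjects who switch machine manufacturer type (Lunar or Hologic". The unit is the subject. Nothing says by which visit a switch must have happened, and nothing keeps scans taken before it.

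SAP 9.5.2.1 gives the main model. Percent change from baseline to each visit "will be based on an ANCOVA model with treatment as the main effect and baseline value of corresponding parameter as a covariate". For the continuous BMD summary and for this ANCOVA it adds: "This analysis will be repeated including subjects who switch machine manufacturer type (Lunar or Hologic), for subjects with scans only on Lunar machines", with a matching Hologic-only repeat. The same section plans two further analyses without any such repeat:

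- chi-square tests on categories of BMD decrease at Months 6 and 12;
- an ANCOVA of percent change from Month 6 to Months 12, 18 and 24.

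On scanning, Protocol 5.3.1.1 states: "DXA scans are required to be performed for all subjects during the Treatment Period at Months 6, 12, 18, 24, 30, 36, 42, and 48". Follow-Up scans come at Months 6 and 12. The same section foresees that the central reader may be unable to give a percent change because a scanner was changed.

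On the data in hand at the 12-month analysis, SAP 2.5 states: "These analyses will include data collected during the Treatment Period (placebo-controlled and open-label Treatment Periods) and the Follow-Up Period up to the data cut-off". Later analyses may be run at Months 24 and 36 (SAP 2.6), and also at Month 48 or other times (Protocol 8.1.5).

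**The concern.** A change of manufacturer spoils a percent change only when the two scans being compared come from different manufacturers. A woman scanned on one manufacturer at baseline, Month 6 and Month 12, and on the other at Month 18, has valid changes at both key visits. A rule that removes her because of the Month 18 scan discards good data from the key comparisons on account of a later event.

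Three things are at stake.

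- **Precision.** The main Month 6 and Month 12 comparisons lose usable women.
- **Stability.** SAP 2.5 and 8.1 make the 12-month analysis final for efficacy endpoints, but say nothing equivalent for BMD. If Month 6 and 12 BMD is tabulated again at a later lock, the set could shrink although no Month 6 or 12 scan has changed.
- **Bone-loss counts.** The categories include a decrease of 8% or more, and under Protocol 5.3.1.1 a woman losing more than 8% stops study drug and enters Follow-Up. If her Follow-Up scan is on the other manufacturer, the literal rule removes her verified Month 12 loss from the only categorical comparison planned for that visit.

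**Working it through.** **What the documents supply.** Arms of 400 (combination), 100 (elagolix alone) and 200 (placebo), and eight post-baseline treatment scans. They give no switch rate, BMD standard deviation, BMD effect or BMD power target. The only power figure is for the responder endpoints. With 400 versus 200 and two-sided α = 0.05, I obtain 99.4% for NMPP (54% vs 35%) and over 99.9% for DYS (59% vs 23%). This agrees with the stated figure of over 90% but does not bear on BMD.

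**Precision with full arms.** SE/SD = √(1/n₁ + 1/n₂):

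- versus placebo: √(1/400 + 1/200) = 0.0866;
- versus elagolix alone: √(1/400 + 1/100) = 0.1118.

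**Avoidable loss on the literal reading.** Assume that a proportion S switches by Month 48, with the same chance at each of the eight scans, equally in all arms, with no dropout and all switches known. Then:

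- chance per scan: h = 1 − (1 − S)^(1/8);
- switched by Month 6: h; by Month 12: 1 − (1 − h)²;
- valid changes lost at a visit: S minus the proportion switched by that visit;
- SE ratio, excluding all switchers versus excluding only those switched by the visit: √[(1 − switched by visit)/(1 − S)].

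| S (assumed) | Switched by Month 6 | Switched by Month 12 | Valid Month 6 changes lost (of 600) | Valid Month 12 changes lost (of 600) | SE ratio Month 6 | SE ratio Month 12 |
|---|---|---|---|---|---|---|
| 0.05 | 0.0064 | 0.0127 | 0.0436 (26) | 0.0373 (22) | 1.0227 | 1.0194 |
| 0.10 | 0.0131 | 0.0260 | 0.0869 (52) | 0.0740 (44) | 1.0472 | 1.0403 |
| 0.20 | 0.0275 | 0.0543 | 0.1725 (103) | 0.1457 (87) | 1.1025 | 1.0873 |

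The 600 are the combination and placebo arms together. At the 12-month lock only switches up to the cut-off are known, so the loss there is smaller.

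**A by-period reading.** If only switches within the 12-month placebo-controlled period count, Month 12 loses nothing avoidable. Month 6 still loses women who switch at Month 12. At S = 0.10 that is 0.0260 − 0.0131 = 0.0129 of women, with an SE ratio of √(0.9869/0.9740) ≈ 1.007.

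**What each planned analysis does with a woman who switches after Month 12 (literal reading).**

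| Analysis | Her valid Month 6/12 changes | Cross-manufacturer changes of earlier switchers |
|---|---|---|
| Main ANCOVA | dropped | dropped |
| ANCOVA repeat including switchers | kept | also kept |
| Lunar-only and Hologic-only repeats | dropped | dropped |
| Chi-square on decrease categories | dropped, no repeat | dropped |
| Month 6-referenced ANCOVA | Month 6-to-12 change dropped, no repeat | dropped |

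No row is stated to keep every valid change and only valid changes.

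**The case against.** **The SAP does not say that a switch at any time counts.** A reader might infer that it does, and the wording about scans on only one manufacturer, which sorts women by scan history, makes that the natural reading. It is not the only one. SAP 9.1 reports the placebo-controlled and open-label periods separately, and SAP 9.5.2.1 places the Month 6 and 12 comparisons within the placebo-controlled period. Judging switcher status by period or by visit is not ruled out. SAP 2.5 says which data are in the lock, not which scans decide membership of the analysis. This stands, and it is itself a reason to write the rule down.

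**The planned repeat goes far towards restoring the lost scans.** A reader might infer that pre-switch scans vanish from every Month 6 and 12 comparison. They do not. The ANCOVA repeat brings them back, and the only cross-manufacturer changes it admits at a visit come from women already switched by then, about 1.3% at Month 6 and 2.6% at Month 12 when S = 10%. This stands for the ANCOVA. It does not help the two analyses that have no repeat.

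**Bias is not shown.** A reader might infer that women who stay longer are selectively removed, because more scans mean more chances to switch. But women who discontinue at or after Month 6 also have Follow-Up scans, and no passage links a manufacturer change to arm or bone outcome.

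**The simple inflation 1/√(1 − S) overstates the loss.** At S = 10% it gives 5.4%, but it compares with excluding nobody. A scan-level rule would also drop changes already spoiled by the visit, so the avoidable part is 4.7% at Month 6 and 4.0% at Month 12.

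**BMD lies outside the fixed-sequence testing** (SAP 10.0), so no confirmatory claim turns on this. That is correct, although the protocol still calls these comparisons key.

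**Conclusion.** The concern holds in a limited form. The default exclusion is by subject and has no timing rule. On its natural, literal reading it removes valid same-manufacturer Month 6 and 12 changes of later switchers from the main ANCOVA, from the categorical tests and, for Month 6-to-12, from the Month 6-referenced ANCOVA. Only the first of these has a repeat including switchers, and that repeat mixes in cross-manufacturer changes.

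The size depends on a switch rate that the documents do not give. The avoidable inflation of roughly 2% to 10% at Month 6 and 2% to 9% at Month 12 rests on assumed switching of 5% to 20%, evenly spread, with no dropout and every switch to Month 48 known. It is less at the 12-month lock, and under a by-period reading it is close to nil. This is a modest loss of precision and reproducibility. The documents do not support a finding of bias, or that the Month 6 and 12 comparisons are invalid.

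**What to change.** Replace the subject-level exclusion in SAP 9.5.2 with a scan-pair rule: omit a percent change only when its two scans, the visit scan and that analysis's own reference scan, come from different manufacturers; keep all other scans.

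The reference should be the one each analysis uses: the Day 1 baseline, the reset baseline for women first given placebo (SAP 9.1, Protocol 8.1.7.1), or Month 6. Tying the rule to the original baseline alone would discard valid pairs. For example, a woman who switches before Month 6 and stays on the new manufacturer has a valid Month 6-to-12 change.

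Apply the rule to the percent-change ANCOVA, the categorical BMD-decrease tests and the Month 6-referenced ANCOVA. Keep the existing repeat including switchers as a sensitivity analysis, and report by arm and visit how many changes the rule omits.

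The cost is one sentence in the SAP and a flag on each scan pair. The small downside is that the women analysed may differ slightly between visits.

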9.5.2.1 Bone Mineral Density during the Treatment Period

BMD

A summary of continuous BMD at each scheduled assessment will be provided during the appropriate Treatment Period. This summary will include the sample size, mean, SD, median, minimum, and maximum. This analysis will be repeated including subjects who switch machine manufacturer type (Lunar or Hologic), for subjects with scans only on Lunar machines, and for subjects with scans only on Hologic machines.

The analysis of percent change in BMD from baseline to each relevant visit during the Treatment Period will be based on an ANCOVA model with treatment as the main effect and baseline value of corresponding parameter as a covariate. Elagolix plus E2/NETA group will be compared to placebo at Months 6 and 12 and will be compared to the

elagolix alone group at Month 6 during the placebo-controlled Treatment Period. In addition, elagolix alone group will be compared to placebo at Months 6 and 12 during the placebo-controlled Treatment Period. This analysis will be repeated including subjects who switch machine manufacturer type (Lunar or Hologic), for subjects with scans only on Lunar machines, and for subjects with scans only on Hologic machines.

The number and percentage of subjects with percent change from Baseline to each scheduled assessment during the Treatment Period in mutually exclusive categories of BMD decrease: $\leq 0\%$, $> 0\% - \leq 1.5\%$, $> 1.5\% - \leq 3\%$, $> 3\% - \leq 4\%$, $> 4\% - \leq 5\%$, $> 5\% - < 8\%$, and $\geq 8\%$ will be summarized by treatment group. Elagolix plus E2/NETA group will be compared to placebo at Months 6 and 12 and will be compared to elagolix alone group at Month 6 during the placebo-controlled Treatment Period using chi-square tests. In addition, elagolix alone group will be compared to placebo at Months 6 and 12 during the placebo-controlled Treatment Period.

The analysis of percent change in BMD from Month 6 to Month 12 during the Treatment Period will be based on an ANCOVA model with treatment as the main effect and Month 6 BMD values of corresponding parameter as a covariate for subjects who have both Month 6 and Month 12 BMD values. Same analyses will be provided for percent change in BMD from Month 6 to Month 18 and Month 24. Each elagolix group will be compared to placebo.

Cross-tabulation of the DXA scans performed versus Treatment Period completion will be provided after all subjects complete the Treatment Period or premature discontinuation from the Treatment Period.

Listings of subjects meeting the following criteria during the Treatment Period will be provided:

- Listing of subjects with BMD decrease $\geq 8\%$

In addition, the following plot will be provided as needed:

- Percent change from Baseline to each scheduled assessment (Months 6, 12, 18, 24, 30, 36, 42, 48) during the Treatment Period in BMD vs. Baseline BMD values for subjects with greater than 8% BMD decrease at any location during the Treatment Period.
- Cumulative distribution function of percent change from baseline in BMD at each scheduled assessment (Months 6, 12, 18, 24, 30, 36, 42, 48) during the Treatment Period.
- Percent change from Baseline to each scheduled assessment (Months 6, 12, 18, 24, 30, 36, 42, 48) in BMD during the Treatment period.

Z-Score and T-Score

A continuous summary of the Z-score and T-score at each scheduled assessment will be provided by treatment group during the Treatment Period. This summary will include the sample size, mean, SD, median, minimum, and maximum.

A categorical summary of Z-score will be provided at each scheduled assessment during the Treatment Period for the following categories: ≤ -2.0 , > -2.0 to ≤ -1.5 , > -1.5 to ≤ -1.0 , and > -1.0 . A categorical summary of T-score will be provided at each scheduled assessment during the Treatment Period for the following categories: ≤ -2.5 , > -2.5 to < -1.0 , and ≥ -1.0 . In addition, a categorical summary of the worst Z-score and T-score during the Treatment Period for the above categories will be provided.

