DXA scans of the lumbar spine, total hip, and femoral neck will be obtained at Follow-Up Months 6 and 12.

COVID-19 Pandemic-Related Acceptable Protocol Modifications

Due to the COVID-19 pandemic, if the subject is unable to complete the DXA at its scheduled time, it can be delayed up to one month. Should the delay be longer, AbbVie should be notified for further guidance.

Endometrial Biopsy

Endometrial biopsies will be performed during the Screening and Treatment Periods, as indicated in Appendix C. Instructions on endometrial biopsy collection, processing and shipping procedures will be provided by the central laboratory selected for this study. All central laboratory pathologists will be blinded to the subjects' treatment group assignments. Endometrial biopsies will be independently read by two qualified central laboratory pathologists. If the results are discrepant, the biopsy will be read by a third central laboratory pathologist to facilitate resolution and the worst case reading (of all three reads) will be taken as the final diagnosis. A final pathology report containing the final diagnosis from the central laboratory will be issued to the Investigator in all cases.

Prior to performing the endometrial biopsy, a negative urine pregnancy result must be obtained on the day of the procedure. Pre-medication for the endometrial biopsy procedure is allowable, e.g., at the investigator's discretion, misoprostol for cervical dilation is allowable. In addition, lidocaine may be used as local anesthesia on the cervix. Any medications used for the procedure should be recorded in source documents and on the appropriate eCRF. The Investigator should write a brief procedure note in the source

documentation noting the depth of placement of the Pipelle during the procedure. If an endometrial biopsy cannot be performed because of anatomical reasons, the AbbVie TA MD should be consulted for further guidance.

If the endometrial biopsy is performed on the same day as the Pap test or transvaginal ultrasound, the endometrial biopsy should be performed after the Pap test and transvaginal ultrasound.

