9.0 Safety Analyses

9.1 General Considerations

Safety summaries will be provided separately using the Safety Analysis Set during the placebo-controlled Treatment Period, Safety Analysis Set during the open-label Treatment

Period, and All Elagolix plus E2/NETA Analysis Set as defined in Section 4.0. Unless otherwise specified, no statistical comparisons or tests will be performed on Safety Analysis Set during the open-label Treatment Period or the All Elagolix plus E2/NETA Analysis Set.

Unless otherwise specified, the baseline for the 12-month placebo-controlled Treatment Period will be the last non-missing value obtained prior to or on Study Day 1. The baseline during the open-label Treatment Period will be the last non-missing value obtained prior to or on the initiation day of elagolix (either elagolix alone or elagolix plus E2/NETA). The baseline for All Elagolix plus E2/NETA Analysis Set will be the last non-missing value obtained prior to or on the initiation day of elagolix plus E2/NETA.

All safety analyses will be based on observed data. Unless otherwise specified, missing data will not be imputed.

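### Per-visit observed-case ANCOVA for BMD describes women still on drug; after Month 6 it understates the bone loss expected for all who start, increasingly so towards Month 48

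*SAP*

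**What the plan says.** - **Model.** SAP 9.5.2.1: "percent change in BMD from baseline to each relevant visit during the Treatment Period will be based on an ANCOVA model". The terms are treatment and baseline BMD; earlier post-baseline scans do not enter. The planned repeats concern scanner manufacturer only.
- **Missing data.** SAP 9.1: "All safety analyses will be based on observed data. Unless otherwise specified, missing data will not be imputed". SAP 8.2 defines an MMRM, but only for efficacy.
- **Open-label restriction.** SAP 4.0 leaves women who do not enter the open-label period out of its analyses.
- **Scans.** Protocol 5.3.1.1 has DXA "required to be performed for all subjects during the Treatment Period at Months 6, 12, 18, 24, 30, 36, 42, and 48".
- **Stopping rule.** The same section lists a low Z- or T-score, or "a BMD decrease from baseline of > 8% in the lumbar spine, total hip" or femoral neck. On either result before Month 48, "the subject must be discontinued from study drug dosing and will enter the Follow-Up Period". Protocol 5.4 repeats the rule.
- **After removal.** For these women "additional DXA scans do not need to be performed as a part of the Premature Discontinuation visit procedures". Their next scans "will be obtained at Follow-Up Months 6 and 12", are off drug, and are summarised under SAP 9.5.2.2.
- **Where testing happens.** Protocol 8.1.7.4 makes lumbar spine at Months 6 and 12 the key comparison. Change from baseline at later visits is summarised without between-group tests. SAP 9.5.2.1 also compares each elagolix group with placebo on change from Month 6 to Months 12, 18 and 24.

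**The concern.** Whether a woman is scanned on drug at a later visit depends partly on her own earlier BMD result. A model that uses only baseline BMD and the current visit discards the values that explain why she is absent. BMD change is positively correlated over time within a woman, so those removed would on average have had below-average BMD change at later visits. The mean of those remaining is shifted towards less loss, and the shift grows as removals accumulate over eight visits.

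The per-visit loss categories and the cumulative distribution plots share the problem: a woman removed after a Month 18 scan is absent from both at Months 24 to 48. The ANCOVAs starting from Month 6 drop women whose Month 6 scan triggered the rule.

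At stake is how the 48-month bone results are read. The third objective (Protocol 4.0) is continued safety for up to 48 months, and the shift favours the product.

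**Working it through.** **The plan's own figures.** The plan states no BMD mean, SD, expected removals or BMD power. Its only design figure is power above 90% for the pain responders. This reproduces (99.4% for NMPP, over 99.9% for DYS with 400 versus 200) but does not bear on BMD. Everything below rests on assumed BMD values.

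**Month 6.** No DXA-driven removal can precede the first on-treatment scan, so the bias from the rule is zero.

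**Month 12, by formula, one site.** Let Month 6 change have mean μ and SD s, and let r be the Month 6 to Month 12 correlation. With a = (-8 - μ)/s, removing women below -8% shifts the Month 12 mean by r·s·φ(a)/(1 - Φ(a)).

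- Assume between-woman SD 2.2 and measurement SD 1.5. Then s = √(2.2² + 1.5²) = √7.09 = 2.66 and r = 4.84/7.09 = 0.68.
- μ = -0.8: a = -7.2/2.66 = -2.70, φ = 0.0103, and the shift is 0.68 × 2.66 × 0.0103/0.997 = 0.02 points.
- μ = -2.5 (assumed for the arm starting on elagolix alone): a = -5.5/2.66 = -2.07, φ = 0.0473, and the shift is 0.68 × 2.66 × 0.0473/0.981 = 0.09 points.

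Letting any of three sites trigger removal raises these by simulation to about 0.03-0.05 and about 0.16. Wider one-site inputs (s 2.5-3.5, r 0.6-0.9) give 0.01-0.17 for μ of -0.5 to -1, and 0.05-0.49 for μ of -2.5 to -3.

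**Months 12 to 48, by simulation.** Assumptions: Month 6 mean -0.8%, mean slope -0.2 or -0.5% per year, the SDs above, 6% random dropout per six months, and removal for more than 8% loss at any of three sites (Z/T rule not modelled). Bias is the observed-case mean minus the mean had everyone continued. Removed is the share the rule alone would take out before Month 48. The rows use a between-site correlation of 0.6 and count six months as half a year, so the true Month 48 mean is -0.8 - 0.2 × 3.5 = -1.50 or -0.8 - 0.5 × 3.5 = -2.55.

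| Mean slope | Between-woman slope SD | True Month 48 mean | Bias Month 12 | Bias Month 48 | Removed | Bias left by likelihood model, Month 48 |
|---|---|---|---|---|---|---|
| -0.2 | 0 | -1.50 | 0.04 | 0.19 | 5.6% | 0.02 |
| -0.5 | 0 | -2.55 | 0.04 | 0.29 | 9.3% | 0.02 |
| -0.2 | 1.0 | -1.50 | 0.04 | 0.93 | 16.3% | 0.10 |
| -0.5 | 1.0 | -2.55 | 0.04 | 1.21 | 22.7% | 0.12 |

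Varying the between-site correlation from 0.3 to 0.9 gives Month 48 bias of about 0.15-0.3 with slope SD 0 (about 4-10% removed) and about 0.8-1.2 with slope SD 1 (about 13-25% removed). With the protocol's 28-day months the span is 42 × 28/365.25 = 3.22 years, the true means are -1.44 and -2.41, and the slope-SD-1 range falls to about 0.7-1.0.

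**A second set of assumptions.** Month 48 mean -1% to -3%, SD rising from 2.5 to 3.5 or from 3 to 4, adjacent-visit correlation 0.9, Z-score rule included in most runs. Bias was 0.01-0.11 at Month 12, 0.07-0.40 at Month 24, 0.17-0.78 at Month 36 and 0.32-1.21 at Month 48, with 7-29% removed. In one run a true mean of -2.00% appeared as -1.48% with 13% removed. A likelihood model using earlier scans left about 0.00. In two steep-loss runs with 48% and 70% removed, the uncorrected bias was 2.7 and 6.2 points, and the single-site likelihood model still left 0.3 and 0.9.

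**The case against.** The strongest reply has four parts.

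1. **The tested comparisons are barely touched.** A reader might infer that the second objective, BMD at Months 6 and 12, is compromised. The documents do not support that. Month 6, including the comparison with elagolix alone, is unaffected by the rule. The Month 12 shift is a few hundredths of a point for the combination arm, and any shift in placebo offsets part of it. This stands. The exception is Month 12 results for the arm that started on elagolix alone.
2. **The observed mean is not wrong for what it describes.** It validly describes women still on drug, and SAP 4.0 makes that restriction deliberately. A repeated-measures model estimates a hypothetical mean, as if removed women had continued dosing, which the protocol does not allow. This stands: it is a reason to add the model, not to replace the ANCOVA.
3. **Removed women stay visible.** It would be wrong to infer that they vanish. The triggering scan counts at its own visit. The SAP also plans a listing of decreases of 8% or more, worst Z- and T-score categories, a table of scans against completion, and follow-up summaries by time of discontinuation. This stands in part: none of these corrects a visit mean, and there is no cumulative or worst-value table for percent change.
4. **The size is assumption-driven.** A Month 48 bias near 1 point might be read as established. It is not: in the tabulated model it appears only when women differ appreciably in rate of loss, and the documents give nothing to settle that.

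**Conclusion.** The point holds as a limitation of interpretation with a cheap remedy. The mechanism and its direction follow from the documents together with the positive within-woman correlation of BMD change. After Month 6, the planned means understate the loss expected for all who start, and the gap widens with time.

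The size is nil at Month 6. At Month 12 it is likely to be negligible for combination versus placebo and larger, about 0.16 points under an assumed Month 6 mean of -2.5%, for the arm that began on elagolix alone. By Month 48 it could be anywhere from a minor to a material fraction of the reported loss, depending on how much women differ in rate of loss and how many the rule removes. The documents support neither a claim that the key comparisons are invalid nor a single figure for the late bias.

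**What to change.** Add to SAP 9.5.2.1, leaving the stopping rule and the planned ANCOVA as they are:

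- An MMRM of percent change in BMD (treatment, visit, treatment-by-visit, baseline BMD, unstructured covariance) on all on-treatment scans of all treated women. Report its Month 12 contrasts and later LS means beside the ANCOVA.
- A statement that the SAP 4.0 open-label exclusion does not apply to this model. Because SAP 9.1 resets the placebo arm's baseline, fit that arm's open-label data separately from the reset baseline.
- The number removed by the DXA rule before each visit, and the cumulative proportion with more than 8% loss at any time.
- A joint three-site model or a last-on-treatment-scan sensitivity analysis, because removal can be triggered at another site or by Z- or T-score.

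The cost is SAP wording, one extra model per site, the sensitivity analysis and two simple tables, all from scans already collected. The MMRM relies on missing-at-random, which a single-site model meets only approximately. Because it targets the hypothetical mean, the observed-case ANCOVA should stay as the description of women still on drug.
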